ATTACHMENT 4 ADVERSE EVENTS REPORTING FORM	
ATTACHMENT 5 DATA MONITORING COMMITTEE CHARTER	

CONFIDENTIAL

This material is the property of the Seattle Children's Research Institute. Do not disclose or use except as authorized in writing by the study sponsor-investigator.

List of Abbreviations

AE: adverse event
AHA: American Heart Association
AAP: American Academy of Pediatrics
AST: aspartate aminotransferase
ALT: alanine aminotransferase
CBC: complete blood count
CHO: Chinese hamster ovary
CHRMC: Children's Hospital and Regional Medical Center
CRC: Children's Research Institute Clinical Research Center
CRF: case report form
CRP: C-reactive protein
DMC: Data Monitoring Committee
DNA: deoxyribonucleic acid
Echo: echocardiogram
EKG: electrocardiogram
ESR: erythrocyte sedimentation rate
FDA: Federal Drug Administration
HIPAA: Health Insurance Portability and Accountability Act of 1996
Ig: immunoglobulin
IV: intravenous
IVIG: intravenous immunoglobulin
IRB: Institutional Review Board
KD: Kawasaki Disease
PCRC: Pediatric Clinical Research Center
PHI: private health information
PI: Principal Investigator
PK: pharmacokinetics
PPD: purified protein derivative
SAE: serious adverse event
TNF: tumor necrosis factor
TNFR: tumor necrosis factor receptor

CONFIDENTIAL

This material is the property of the Seattle Children's Research Institute. Do not disclose or use except as authorized in writing by the study sponsor-investigator.

Study Summary

Title	Etanercept in Kawasaki Disease	
Study Phase	Clinical phase II study	
Methodology	Randomized double blind placebo controlled clinical study	
Study Duration	4 years	
Study Centers	Children's Hospital and Regional Medical Center, Primary Children's Medical Center, Children's Hospital of Wisconsin, Sainte-Justine Hospital, Steven & Alexandra Cohen Children's Medical Center of New York, Texas Children's Hospital, Columbia University Medical Center, and Montefiore Medical Center.	
Objectives	Determine if etanercept (0.8 mg/kg, maximum 50 mg) given subcutaneously reduces IVIG refractory rate and retreatment rate in the KD patient population.	
Number of Subjects	196	
Diagnosis and Main Inclusion Criteria	Patients aged 2 months to 20 years of age presenting with Kawasaki Disease as defined by the American Academy of Pediatrics and the American Heart Association.	
Study Product, Dose, Route, Regimen	Etanercept (trade name: Enbrel) 3 weekly subcutaneous injections at 0.8 mg/kg dosage	

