Adverse events will be tabulated for each treatment group by severity, relationship to study drug and body system affected (according to the NCI CTC grading and MEDDRA classification system). The outcome of any SAE episodes that occur will be summarized. Adverse event rates will be compared between treatment groups using Poisson or negative binomial regression modeling. The proportions of subjects experiencing an adverse event of any type and the proportions experiencing an SAE will be compared using chi-square or Fisher's Exact testing.

Pharmacokinetic analyses: PK analyses will be performed after completion of the study and unblinding, so as not to unblind study investigators. Samples from patients receiving etanercept will be forwarded to the Seattle site for storage and then later submitted to Amgen for determination of serum drug concentrations. Peak and trough analyses will be performed. Drug clearance, volume of distribution and $\frac{1}{2}$ life will be determined using etanercept modeling and algorithms⁴¹ and loaded on SAAM2 software available at the University of Washington.

CRP and other standard laboratory studies will be performed in the clinical laboratory of each participating hospital. Serum cytokines, IL-3, IL-6, and TNF α will be performed in Center of Developmental Therapeutics at Children's Hospital Research Institute in Seattle. Assay will be performed on Luminex-200 multiplex system, which resides in center.

8 Safety and Adverse Events

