All unresolved adverse events should be followed by the investigator until the events are resolved, the subject is lost to follow-up, or the adverse event is otherwise explained. At the last scheduled visit, the investigator should instruct each subject to report any subsequent event(s) that the subject, or the subject's personal physician, believes might reasonably be related to participation in this study.

Abnormal Laboratory Values

A clinical laboratory abnormality should be documented as an adverse event if any one of the following conditions is met:

- The laboratory abnormality is not otherwise refuted by a repeat test to confirm the abnormality
- The abnormality suggests a disease and/or organ toxicity
- The abnormality is of a degree that requires active management; e.g. change of dose, discontinuation of the drug, more frequent follow-up assessments, further diagnostic investigation, etc.

Hospitalization, Prolonged Hospitalization or Surgery

Any adverse event that results in hospitalization or prolonged hospitalization should be documented and reported as a serious adverse event unless specifically instructed otherwise in this protocol. Any condition responsible for surgery should be documented as an adverse event if the condition meets the criteria for an adverse event.

Neither the condition, hospitalization, prolonged hospitalization, nor surgery are reported as an adverse event in the following circumstances:

- Hospitalization or prolonged hospitalization for diagnostic or elective surgical procedures for a preexisting condition. Surgery should **not** be reported as an outcome of an adverse event if the purpose of the surgery was elective or diagnostic and the outcome was uneventful.
- Hospitalization or prolonged hospitalization for therapy of the target disease of the study, unless it is a worsening or increase in frequency of hospital admissions as judged by the clinical investigator. (Note: This study population includes a notable proportion of patients requiring hospital readmissions due to refractory IVIG therapy. A clear definition of a *serious adverse event* relating to readmissions will be determined at the Organizational Meeting with the Data Monitoring Committee.)

Expected Adverse Events

The following AEs are expected with Kawasaki Disease and IVIG:

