Fever, chills, sore throat, chest tightness, rash, redness of the eyes, vomiting, diarrhea, headache, nausea, irritability, meningismus, anaphylaxis or hypersensitivity, hypotension, rash, skin peeling or desquamation, extremity swelling, coronary arteritis, coronary aneurysms, myocardial infarction, myocarditis, mitral regurgitation, pericarditis, hydropic gall bladder, joint swelling or pain, lymphadenopathy, arrhythmias, blood clots.

Lab abnormalities; elevated CRP and ESR; thrombocytosis, hypoalbuminemia, anemia, pyuria, elevation of liver transaminases.

Additionally, localized redness and swelling at injection site are expected AEs for etanercept. A full list of AEs is included in the Etanercept package insert.

Serious Adverse Events expected are readmission due to recurrent or persistent fever.

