10.3 Timing And Purpose Of The DMC Meetings

Organizational Meeting

The initial meeting of the DMC will be an Organizational Meeting. It will be held during the final stages of protocol development, to provide advisory review of scientific and ethical issues relating to study design and conduct, to discuss the standard operating procedures for the role and functioning of the DMC, and to discuss the format and content of the Session Reports that will be used to present trial results at future DMC meetings. The Organizational Meetings will be attended by the DMC and the lead trial investigators. The DMC will be provided the drafts of the clinical trial protocol, the DMC Charter, and the current version of the case report forms. The DMC will also receive the initial draft of the Session Reports.

Interim Safety/Trial Integrity Reviews

One or more 'Safety/Trial Integrity Reviews' will be held during the progress of the study to review safety information and to review factors relating to quality of trial conduct. Unless circumstances necessitate otherwise, these meetings will be held by phone and be attended by all members of the DMC. The DMC will meet at least every 6 months.

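### The between-arm SAE test does not separate hospitalisations for refractory KD, so where these are recorded as SAEs it partly measures efficacy

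*Combined protocol and SAP*

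**What the plan says.** All references are to the combined protocol and SAP.

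- **Efficacy outcome.** Section 7 counts a patient as refractory when fever persists beyond 36 hours after IVIG, or recurs within 10 days, and the clinician decides to retreat with IVIG.
- **What is serious.** Section 8.1 counts an event as serious if it causes or prolongs a hospital stay. It exempts admission or a longer stay for treatment of the target disease, "unless it is a worsening or increase in frequency of hospital admissions as judged by the clinical investigator". It adds: "This study population includes a notable proportion of patients requiring hospital readmissions due to refractory IVIG therapy". The SAE definition "relating to readmissions will be determined at the Organizational Meeting with the Data Monitoring Committee".
- **Expected events.** The list of expected events in Section 8.1 ends: "Serious Adverse Events expected are readmission due to recurrent or persistent fever".
- **Timing of the DMC meeting.** Section 10.3 says of the Organizational Meeting: "It will be held during the final stages of protocol development". The contents list names Attachment 5, "DATA MONITORING COMMITTEE CHARTER", which is not in the supplied text.
- **Safety analysis.** Section 7 says: "Adverse events will be tabulated for each treatment group by severity, relationship to study drug and body system affected". It models overall AE rates, and "the proportions experiencing an SAE will be compared" by chi-square or Fisher's exact test. Hospitalisations for refractory disease are not treated separately.
- **Safety focus.** Section 3.2 singles out serious infections, meaning those that need admission. Section 7 names no by-arm estimate for them.

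**The concern.** A refractory patient may be admitted again or kept in longer, and Section 8.1 gives a route by which that stay is an SAE. One clinical event can then count once as an efficacy failure and once as a safety event. If etanercept reduces refractoriness, its SAE proportion falls for that reason alone. A lower SAE proportion could be read as better safety, and an excess of other SAEs, infections included, could be offset in the total. At stake is what the first secondary aim (Section 2) can conclude. The planned analyses do not supply the figure that would separate the two explanations, nor a named estimate for the infections that Section 3.2 makes the focus.

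**Working it through.** The plan gives no SAE or readmission rate, so there is no figure of its own to reproduce. The check has two parts: what the text allows, and how much it could matter.

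**1. Can refractory disease enter the SAE count?** Section 6.2 says patients usually stay 24 to 48 hours after IVIG. Section 3.3 says refractoriness can appear up to 2 weeks after it. Some failures will therefore arise after discharge and may be readmitted. Others will be retreated in the first stay, and Section 8.1 covers prolonged stays as well. The target-disease exemption works in the other direction. So f, the share of refractory patients recorded as SAEs, is not fixed by the text: 0 and 1 are both possible.

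**2. Illustration of size.** Inputs:
- n = 196/2 = 98 per arm (Section 4), assuming 1:1 allocation.
- Refractory rates r of 25% v 8% and 25% v 15%, both in the tables of Section 4.3, plus 25% v 25% for no effect.
- Other SAEs s = 2% in both arms (assumption). As a rough anchor from another population, the JRA rate in Section 1.2 over 44 days (day-14 dose plus 30 days) gives 0.13 × 44/365 = 1.6%.
- f = 0, 0.25 and 0.5 (assumption), the same in both arms, with the two kinds of event independent.
- Two-sided 5% level (assumption).

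P(any SAE) = 1 − (1 − f·r)(1 − s).

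At f = 0.25:
- placebo: 1 − 0.9375 × 0.98 = 8.1%
- etanercept, r = 8%: 1 − 0.98 × 0.98 = 4.0%
- etanercept, r = 15%: 1 − 0.9625 × 0.98 = 5.7%

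Exact enumeration of two binomials with n = 98 and the uncorrected chi-square test gives the probability that the SAE test significantly favours etanercept when other SAEs do not differ:

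| Refractory rates | f = 0 | f = 0.25 | f = 0.5 |
|---|---|---|---|
| 25% v 8% | 2% | 22% | 51% |
| 25% v 15% | 2% | 10% | 19% |
| 25% v 25% | 2% | 3% | 3% |

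With Fisher's exact test, the entries at f = 0.25 and 0.5 are 15% and 41% in the first row, and 6% and 13% in the second. The third row stays near the nominal 2.5%: with no effect on refractoriness, the added events do not favour etanercept.

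**3. Offsetting.** Assume other SAEs of 2% on placebo and 5% on etanercept. Etanercept shows numerically fewer SAEs in 8% of trials at f = 0. At f = 0.25 and 0.5 this becomes 58% and 86% (25% v 8%), or 40% and 63% (25% v 15%).

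**4. Serious infections.** The JRA rate in Section 1.2 gives 0.04 × 44/365 = 0.0048 per patient, or 0.0048 × 98 ≈ 0.5 expected per arm (again a rough anchor). The Newcombe 95% interval for the difference is ±3.8 percentage points at 0 v 0. At 3 v 0 it is −1.2 to 8.6 points, with Fisher p = 0.25.

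**The case against.** **The rule may already exist.** The meeting that was to settle it falls before the protocol is final, and the charter is not supplied. This stands. A reader might infer that the plan has no rule, or that Section 8.1 contradicts itself. The documents do not show either: the expected-event entry may simply label those readmissions that meet the investigator-judged exception, and so set their reporting category in Table 3. The agreed rule is nonetheless not in the supplied text, and whatever it is, Section 7 does not separate the events it lets in.

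**f may be 0.** This stands, and there is then no distortion. A reader might instead argue that f must be below 1 because some failures are retreated in the first stay. That does not follow, since prolonged stays can also be serious.

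**The any-SAE proportion is a legitimate measure of total burden.** This stands, so the comparison should be kept and the second version added beside it.

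**Infections are not hidden.** This stands. The by-arm body-system tables show them, and the DMC is told to focus on them (Section 8.5.1). What is missing is narrower: severity grade is not seriousness, and no by-arm estimate of serious infections is named.

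**Power is low in any case.** With KD events removed, a difference of 2% v 5% in other SAEs is detected in only 18% of trials (Fisher 9%). This stands, and for harms of that size the gain is descriptive.

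**Conclusion.** The point holds in conditional form. Where hospitalisations for refractory KD are recorded as SAEs and etanercept reduces refractoriness, the planned SAE test carries part of the efficacy effect. With the assumed inputs, the chance of a significant result favouring etanercept without any difference in other SAEs rises from 2% to between 10% and 51% for f of 0.25 to 0.5. Those figures rest on assumed values of f and of the other-SAE rate, and on the planning rates in Section 4.3; they are not predictions. A reader might infer that the SAE test is biased as it stands. The documents do not support that, because they do not fix f and the effect of etanercept is unknown. The consequence is confined to how the overall SAE comparison is read. The primary endpoint is unaffected. The change is worth making because it is cheap and alters what the first secondary aim can conclude.

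**What to change.** 1. In Section 7, report the between-arm SAE comparison twice: with and without hospitalisations attributed to refractory KD. These should cover both readmissions and prolonged first stays, with cause coded while blinded and the events shown in their own row.
2. In Section 7, add serious infections as defined in Section 3.2, by arm, as a difference with a confidence interval. Read it descriptively, because few events are expected.
3. In Section 8.1, reconcile the target-disease exemption and the expected-SAE entry with the rule agreed with the DMC, and state that rule. No particular rule is proposed here. Settling it may change which events are reported.

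The cost is SAP and protocol wording, a few table rows and the blinded coding of cause. The main risk is that an infection is miscoded as KD fever, which is why both versions should be shown.

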8.2 Recording of Adverse Events

At each contact with the subject, the investigator must seek information on adverse events by specific questioning and, as appropriate, by examination. Information on all adverse events should be recorded immediately in the source document, and also in the appropriate adverse event module of the case report form (CRF). All clearly related signs, symptoms, and abnormal diagnostic procedures results should be recorded in the source document, though should be grouped under one diagnosis.

Table 3 Adverse Event (Experience) Reporting Summary

	DMC/DSMB	IRB*	FDA	Investigator(s)/Sponsor
I. RELATED, UNEXPECTED		Requirements may vary according to institution		

CONFIDENTIAL

This material is the property of the Seattle Children's Research Institute. Do not disclose or use except as authorized in writing by the study sponsor-investigator.

Fatal or Life-Threatening	Telephone/email within 24 hours Written notification within 3 working days of telephone report	Written notification within 3 calendar days Follow up reports as soon as information becomes available	Telephone or fax within 7 calendar days Written notification within 15 calendar days using FDA form 3500A per 21CFR312.32	Telephone/email within 24 hours Written notification within 3 working days of telephone report
Serious/severe (including disability)	Written notification within 7 calendar days	Written notification within 15 calendar days.	Written notification within 15 calendar days using FDA form 3500A per 21CFR312.32	Telephone/email within 24 hours Written notification within 3 working days of telephone report
Mild/moderate	As per protocol	Quarterly	Annual report per 21CFR312.33	As per protocol
II. RELATED, EXPECTED				
Fatal, Life-Threatening	Telephone/email within 24 hours Written notification within 3 working days of telephone report	Written notification within 3 calendar days Follow up reports as soon as information becomes available	Telephone or fax within 7 calendar days Written notification within 15 calendar days using FDA form 3500A per 21CFR312.32	Written notification within 7 days
Serious/severe (including disability)	Written notification within 7 calendar days	IRB status report (annual)	Written notification within 15 calendar days using FDA form 3500A per 21CFR312.32	Written notification within 7 calendar days
Mild/moderate	As per protocol	IRB status report (annual)	Annual Report per 21CFR312.33	As per protocol
II. NOT- RELATED				
Fatal, Life-Threatening	Written notification within 10 days	IRB status report (annual)	Annual Report per 21CFR312.33	Written notification within 10 days

All adverse events occurring during the study period must be recorded. The clinical course of each event should be followed until resolution, stabilization, or until it has been determined that the study treatment or participation is not the cause. Serious adverse events that are still ongoing at the end of the study period must be followed up to determine the final outcome. Any serious adverse event that occurs after the study period and

CONFIDENTIAL

This material is the property of the Seattle Children's Research Institute. Do not disclose or use except as authorized in writing by the study sponsor-investigator.

Table 3 summarizes regulatory guidelines for reporting adverse events.

8.3 Reporting of Serious Adverse Events

8.3.1 DMC Notification by Investigator

Serious adverse events will be reported to [name] within 24 hours of when investigators are first aware of SAE by telephone and/or fax. [name] will forward SAE data to the Data Monitoring Committee within 24 hours. [name] will oversee that the data and safety letter are sent to the appropriate entities within an appropriate time frame.

8.3.2 IRB Notification by Investigator

Reports of all serious adverse events (including follow-up information) must be submitted to the Institutional Review Board (IRB). The timeline of reporting procedures varies by the anticipation level and the severity of the adverse event [see Table]. Copies of each report and documentation of IRB notification and receipt will be kept in the Investigator's binder.

8.4 Stopping Rules

The DMC shall review clinical and laboratory data provided by the Principal Investigator to guide their recommendations regarding termination or continuation of the trial. If the evidence indicates the experimental intervention has an unfavorable benefit-to-risk-profile, the DMC shall recommend termination of the trial.

8.5 Safety Monitoring

It is the responsibility of the Principal Investigator to oversee the safety of the study at his site. This safety monitoring will include careful assessment and appropriate reporting of adverse events as noted above, as well as the construction and implementation of a site data and safety-monitoring plan (see section 10 Auditing, Monitoring and Inspecting). Medical monitoring will include a regular assessment of the number and type of serious adverse events.

8.5.1 Independent Data Monitoring Committee

The Data Monitoring Committee (DMC) will be composed of a pediatric rheumatologist, and a pediatric cardiologist to oversee the study. Safety data of the 196 patients with regards to adverse events, specifically focusing on infections, will be closely monitored in these patients

- *The DMC will meet at least once every 6 months via telephone conference.*
- *The safety data will be supplied to the DMC by the principal investigators team. .*
- *The DMC will prepare minutes to record the summary of its various meetings.*
- *The DMC will appropriately report its findings and/or recommendations to the PI and regulatory bodies.*

The Data Safety Plan and Data Monitoring Committee (DMC)

The data safety plan for this study is also included in detail in the Human Subject section. The DMC was established and chartered in order to monitor the progress of the pilot study. The DMC will continue this

PRIMARY RESPONSIBILITIES OF THE DMC

The DMC will be responsible for safeguarding the interests of trial participants, assessing the safety of the interventions during the trial, and for monitoring the overall conduct of the clinical trial. The DMC will provide recommendations about stopping or continuing the trial. To contribute to enhancing the integrity of the trial, the DMC may also formulate recommendations relating to the selection/recruitment/retention of participants, their management, improving adherence to protocol-specified regimens and retention of participants, and the procedures for data management and quality control.

The DMC will be advisory to the Principal Investigator. The Principal Investigator will be responsible for promptly reviewing the DMC recommendations, to decide whether to continue or terminate the trial, and to determine whether amendments to the protocol or changes in study conduct are required. The Principal Investigator will be required to forward all DMC recommendations to the IRB.

Members

The DMC will be an independent multidisciplinary group consisting of clinicians, whom collectively have experience in the management of patients with Kawasaki Disease and in the conduct and monitoring of clinical trials. Generally, three pediatric subspecialties deal with KD. These are cardiology, rheumatology, and infectious disease. Each of these subspecialties will be represented on the DMC.

